### 4.2.2 Injection/PET Imaging day (Day 1/Visit 1)

### Before administration

Hospitalization will occur on the day of administration of [68Ga]-NeoBOMB1.

For all patients, the following study assessments will be performed on the day of administration of [Ga]-NeoBOMB1:

- Participant will be asked to drink 750 ml of water within 1h before image acquisitions
- Control of dated informed consent
- Review of inclusion and exclusion criteria
- Control of adverse events and concomitant medications
- Physical examination: weight, auscultation of lungs and heart, oral inspection, abdominal palpation
- Vital signs: blood pressure, heart rate
- 12-lead ECG including frequency-corrected QT-time
- Haematology, Blood chemistry, Coagulation parameters: Quick, INR, aPTT, fibrinogen, Urinalysis
- Urine dipstick pregnancy test (in women of childbearing potential)
- Venous blood sampling (~1 ml) for radioactivity assay (only for dosimetry group)
- Urine collection for radioactivity assay (only for dosimetry group)
- Histopathologic evaluation
- Concomitant medications can be administered from 4h after the [Ga]-NeoBOMB1 administration.

### During and after administration

For patients included in the **dosimetry group**, the following safety assessments will take place:

- Vital signs: blood pressure, heart rate immediately after administration of [Ga]-NeoBOMB1, at 30 min after administration and after the last whole-body scan (around 4 h)
- Routine ECG including frequency-corrected QT-time immediately after administration of [Ga]-NeoBOMB1, at 30 min after administration and after the last whole body scan (around 4 h)
- Venous whole blood sampling (~1 ml) for radioactivity assay at 5, 10, 20, 30±5min, 60±5 min and 2h±10 min and 3-4h±10 min.
- Urine collection for radioactivity assay (~1 ml) from 0-2h and from 2-4h. In addition, the subjects will be requested to void immediately.
- Static whole-body PET at 15min, 1h±15 min, at 2h±15 min and at 4h±30 min.

For patients of the **non-dosimetry group**, the following safety assessments will take place:

- Vital signs: blood pressure, heart rate 30 min p.i.
- Routine ECG including frequency-corrected QT-time 30 min p.i.
- Static PET scan between 0 and 5 min only for the prostate subgroup (if applicable)

• Static whole-body PET at 1h30±30 min and at 2h30±30 min

# 4.3 Safety follow-up visits (Day 2/Visit 2, Day 7/Visit 3 and Day 14/Visit 4)

Patients will be discharged on the day 1 after administration of [Ga]-NeoBOMB1 in case of no or minor adverse events that do not contradict such a discharge.

FU visits are scheduled 1 day (Visit 2),  $7\pm1$  days (Visit 3) and  $14\pm2$  days (Visit 4) after administration of [Ga]-NeoBOMB1 and will encompass:

- Physical exam,
- Vital signs,
- 12-lead ECG
- Blood sampling to determine haematological and biochemical parameters,
- Dipstick test for urinalysis
- Check-up of concomitant medication,
- Assessment for adverse events.

On Day 2, patients included in the **non-dosimetry group** will receive a FU phone call to assess any potential adverse events, allergic reactions and concomitant treatments. For this group of patients, Day 7±1 is an optional FU physical visit and can be replaced by a phone call to assess any potential adverse events, allergic reactions and concomitant treatments.

### 4.4 Optional routine clinical disease follow-up

If available, within 3 months from IMP injection, data generated from the routine clinical followup of the patients in the frame of routine patients' management will be collected to help with the interpretation of previous focal uptake of [Ga]-NeoBOMB1 PET which was not corresponded to detectable morphological lesions on CT/MRI

### 4.5 Visit and Assessment Schedule

### Phase II dosimetry group:

A005D-E01-201		Page 45 of 73		
Study Protocol				

Time point		Visit 0 Screening			F	Visit PET Imagi					Visit 2 FU	Visit 3 FU	Visit 4 FU	Optional routine clinical disease FU 
	Day	-28 to -1				1					2	7±1	14 ±2	Max 90
Examination/Evaluation	HH:mm		Pre- dose	0-5 min	5-15 min	20 min	30 min	1h	2h	3-4h				
Informed Consent		•												
Inclusion / Exclusion criteria 		•												
General														
Demographic Data		•												
Medical History		•	•											
Physical Exam		•	•								•	•	•	
Vital Signs		•	•	•			•			•	•	•	•	
Blood analysis (hemato, bi coagulation)	ochemistry,	•	•								•	•	•	
Urine analysis 		•	٠								•	•	•	
Pregnancy Test 		•	•											
12-lead ECG		•	•	•			•			•	•	•	•	
Concomitant Medications		•	•								•	•	•	•
Baseline findings / Adverse Ev	/ents	•				•					•	•	•	•
IMP Administration & Dosim	etry													
[68Ga]-NeoBOMB1 Injection				•										
Blood sampling / radioactivity 			•	•	•	•	•	•	•	•				
Urine collection / radioactivity 			•				•							
[  Ga]-NeoBOMB1 PET/CT in	naging													
Static, whole Body 					•			•	•	•				
GRPR expression assessmen	t 							•						

1. Standard conventional imaging required

2. Urine dipstick test

3. Negative urine pregnancy test at Baseline and within 24 hours prior to administration.

4. Time-points: pre-injection, 5, 10, 20, 30±5, and 1h±5min, 2h±10min, 3-4h±10min post-injection

5. Time-points: pre-injection, from 0-2h and from 2-4h post-injection

6. WB PET/CT: low-dose CT, non-enhanced CT from the vertex to the upper thighs for attenuation correction followed by a total-body PET examination

A005D-E01-201		Page 46 of 73			
Study Protocol					

Any relevant data generated from the routine clinical disease follow-up will be collected: CT/MRI, biopsy, physical examination
 GRPR expression assessment must be performed within 4 weeks after IMP injection

#### Phase II non-dosimetry group:

Time point		Visit 0 Screening		Visit 1 PET Imaging Day			Visit 2 FU⁴	Visit 3 FU⁵	Visit 4 FU	Optional routine clinical disease FU 	
Examination/Evaluation	Day	-28 to -1				1		2	7±1	14±2	Max 90
	HH:MM		Pre-dose	0-5 min	30 min	1h30±30min	2h30 ± 30 min				
Informed Consent		٠									
Inclusion / Exclusion criteria 		٠									
General											
Demographic Data		•									
Medical History		•	•								
Physical Exam		•	•						•	•	
Vital Signs		•	•	•	•				•	•	-
Blood analysis (hemato, bio coagulation)	ochemistry,	•	•						•	•	
Urine analysis 		•	•						•	•	
Pregnancy Test 		•	•								
12-lead ECG		•	•	•	•				•	•	
Concomitant Medications		•	•					•	•	•	•
Baseline findings / Adverse Eve	ents	•			٠			•	•	•	•
IMP Administration											
[68Ga]-NeoBOMB1 Injection				•							
[  Ga]-NeoBOMB1 PET/CT im	aging										
Static scan (prostate cancer -if				•							
Static, whole-body 						•	•				
GRPR expression assessment	3						•				

1. Standard conventional imaging required

2. Urine dipstick test

3. Negative urine pregnancy test at Baseline and within 24 hours prior to administration.

4. Phone call

A005D-E01-201		Page 47 of 73			
Study Protocol					

5. Visit or phone call

6. WB PET/CT: low-dose for 4 WB PET/CT from the vertex to the upper thighs for attenuation correction followed by a total-body PET examination

7. Any relevant data generated from the routine clinical disease follow-up will be collected: CT/MRI, biopsy, physical examination

8. GRPR expression assessment must be performed within 4 weeks after IMP injection

# 5 Study medication

# 5.1 Name and description of Investigational Medicinal Product

The name and pharmaceutical form of the IMP is [Ga]-NeoBOMB1 kit for radiopharmaceutical preparation.

The IMP is a sterile 2-vial kit which consists of:

- Vial 1: NeoBOMB1, 50 μg, powder for solution for injection, to be reconstituted with a solution of gallium-68 chloride (GaCl3) in HCl eluted from a Ge/Ga generator;
- Vial 2: Reaction buffer. Vial 2 is to be added to the reconstituted Vial 1.

The kit has to be used in combination with a solution of 68Ga in HCl provided by a 68Ge/68Ga generator to obtain Ga-NeoBOMB1 solution for injection, being the Radiolabelled Imaging Product, which can be directly injected to the patient.

The volume of Ga-NeoBOMB1 solution for injection, corresponding to the radioactive dose to be administered, is calculated according to the estimated time of injection, on the basis of the current activity provided by the generator and of physical decay of the radionuclide (half-life = 68 min).

It is a mono-dose product.

Vial 1 is a powder for solution for injection containing 50 µg NeoBOMB1 as active ingredient.

The powder is packed in 10 mL Ultra inert Type I Plus glass vials.

Vial 2 Reaction buffer contains no active ingredient.

Reaction buffer solution is contained in a 10 mL cyclic olefin polymer vial.

The kit will be prepared, packaged and released according to Sponsor Standard Operating Procedures (SOPs), Good Manufacturing Practice (GMP) guidelines, ICH GCP guidelines, and applicable local laws/regulations.

# 5.2 IMP administration

[Ga]-NeoBOMB1 must be prepared and administered at the investigational site by appropriately trained personnel.

The lyophilized vial 1 (containing the NeoBOMB1 peptide) shall be directly reconstituted with the GaCl solution in ultrapure HCl provided by a Ge/Ga generator. After addition of the suitable volume of reaction buffer (vial 2) and heating at 95°C for 7 minutes, the Ga-labelled product is ready to use.

Ga eluate should be obtained from an approved commercial Ge/Ga generator that has been eluted within the past 4 hrs.

The recommended activity to be administered is 3 MBq/Kg ( $\pm$  10%), but not more than 250 and not less than 150 MBq.

Refer to Appendix 1 for instruction on the radiolabelling procedure and dispensing [Ga]-NeoBOMB1, cautionary notes, analytical controls and stability of the radiolabelled product.

### 5.3 Dose modifications

Not applicable

### 5.4 Concomitant medication

Patients can be under active systemic treatment such as anti-cancer therapy or hormonal therapy. However, the IP administration should be done at least 72 hours after administration of chemotherapy, to allow for the resolution of any acute side effects. Chemotherapy administration or the start of a new anti-cancer therapy should also be held until 48hrs after IP administration.

Regional/local radiation should be completed at least 2 weeks before administration of IP. Focal radiation therapy is allowed after discussion with the study medical monitor.

The participation of patients on treatment with check-point inhibitors should be discussed with the study medical monitor, to assess concurrent adverse events and side effects prior to administration.

[figure not shown]
Any other allowed concomitant prescribed medications should be discontinued 2h before and until 4h after administration of [Ga]-NeoBOMB1.

[figure not shown]

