### 4.1.5 Routine laboratory exams and pregnancy test

Routine laboratory exams will be performed at all visits except at Day 2 for patients included in the non-dosimetry group.

Clinical Laboratory:

**Blood chemistry**: Non-fasting glucose, Urea, Creatinin, eGFR (calculated), Bilirubin, Na, K, Cl, Ca, GOT (ASAT), GPT (ALAT), γGT, ALP, pancreatic amylase, pancreatic lipase, LDH, CK, CRP, albumin

**Haematology:** Haemoglobin, haematocrit, RBC count, absolute WBC count (neutrophils, eosinophils, basophils, lymphocytes, monocytes), platelets

Coagulation parameters: Quick, INR, aPTT, fibrinogen

Pregnancy test (in women of childbearing potential): dip-stick

Urinalysis via dip-stick: appearance, colour, pH, protein, glucose, blood

The total volume of blood required per patient for standard clinical laboratory assessments will be approximately 16.5 mL for 3 full tubes on each sampling occasion.

Among patients of the **dosimetry group**, routine laboratory exams will be performed at Screening, Day 1, Day 2, Day 7±1 and Day 14±2. In addition, 1 mL of venous whole blood per time-point will be drawn for the biodistribution assessment at Day 1. A total volume of 90.5 mL venous blood will be withdrawn.

Among patients of the **non-dosimetry group**, routine laboratory exams will be performed at Screening, Day 1, Day 7±1 and Day 14±2 for a total volume of withdrawn venous blood of 66 mL.

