# 6.8 Reporting procedures for AEs

A special section is designated to adverse events in the CRF where the following details must be entered:

- Type of adverse event (diagnosis or syndrome; if not known signs or symptoms) and brief description (including context of occurrence)
- Start (date)
- End (date)
- Severity (mild, moderate, severe, life-threatening/disabling, death)
- Serious (no / yes)
- Outcome (resolved, ongoing, ongoing improved, ongoing worsening) and recovery date
- Action taken (none, study medication dose reduced, study medication interrupted, study medication discontinued, medication therapy, surgical procedure, hospitalization, other)
- Relation to study drug (possibly, probably or definitely related or unlikely, probably not related or definitely not related)
- Treatment date with the IMP (in order to estimate the time to onset)

• Patients relevant medical history and/or concomitant treatments that may provide alternative explanation regarding the AEs occurrence.

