#### 5.4 Handling of Missing Data

Missing/Partial Dates:

- In cases of incomplete dates (e.g. AEs and concomitant medications), the missing component(s) will be assumed as the most conservative value possible. No imputation of start/end dates or times will be performed.
  - If a medication date or time is missing or partially missing and it cannot be determined whether it was taken prior or concomitantly, it will be considered both a prior and a concomitant medication.
  - If the partial AE onset date/time information does not indicate that the event started prior to or after the treatment, the event will be classified as treatment-emergent.

- Time from first diagnosis of primary cancer (months) is calculated as (date of administration of the study drug date of first diagnosis + 1)/30.4375. If the month and year of the first diagnosis are provided but the day is missing, the missing day is imputed as 15. If only the year is provided, then the missing month and day are imputed as July 1st for the calculation.
- Actual data values as they appear in the original case report forms (CRFs) will be presented in the data listings.

Other Missing Values: Missing values for other individual data points will remain as missing unless otherwise specified. Missing values will not be imputed and only observed values will be used in data analyses and presentations unless otherwise stated.

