#### 8.1 Adverse Events

AEs will be coded using MedDRA version available at the time (updated biannually).

Treatment-emergent adverse events (TEAEs) are defined as AEs that start on or after the initiation of IMP administration.

Intensity of all adverse events will be graded according to the Toxicity Grading Scale in vaccine clinical trials. Adverse events not listed in the Toxicity Grading Scale in vaccine clinical trials should be graded as guided in study protocol.

An overview of AEs will be provided which summarizes subject incidence of the following information:

- Any TEAEs,
- Drug-related TEAEs,
- Grade 3/4/5 TEAEs,
- Drug-related grade 3/4/5 TEAEs,
- Deaths due to AEs,
- Treatment-emergent SAEs,
- Drug-related treatment-emergent SAEs,
- Dose interruption due to TEAEs, and
- Dose interruption due to drug-related TEAEs.

The number and percentage of subjects with TEAEs will be summarized by SOC and PT. Drugrelated TEAEs, treatment-emergent SAEs, drug-related treatment-emergent SAEs, TEAEs leading to dose interruption of study drug, and drug-related TEAEs leading to dose interruption of study drug will be summarized in the same manner. For these summaries, subjects with multiple adverse events will be counted only once per SOC and PT. Note that drug-related AEs include the AEs which either definitely, probably, or possibly related to study drug.

Summaries will be provided by the worst toxicity grade, SOC, and PT for the number and percentage of subjects with TEAEs and drug-related TEAEs. For these summaries, subjects with multiple adverse events will be counted only once by the worst toxicity grade within each SOC and PT.

Data listings will be provided for SAEs, grade 3/4/5 AEs, AEs leading to dose interruption, Hypersensitivity (SMQ) AEs, and AEs leading to death. A by-subject AE data listing including, but not limited to, verbatim, PT, SOC, toxicity grade, action taken, outcome, and relationship to study drug will be provided.

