#### 8.2 Safety Laboratory Parameters

Descriptive statistics will be provided at baseline and each scheduled visit for selected clinical laboratory test results (chemistry, hematology, and coagulation) and changes from baseline to each scheduled visit will be derived. The minimum post-baseline value, maximum post-baseline value, and last post-baseline value will be summarized in the same manner, where both scheduled and unscheduled post-baseline values will be considered for the derivations.

Laboratory values will be assigned toxicity grades when available using the Toxicity Grading Scale in vaccine clinical trials. Directional shifts in laboratory toxicity grades (comparing baseline grade with the worst post-baseline grade) will be analyzed using standard shift tables, presenting number and proportion of subjects and their maximum grade shift. For parameters without a toxicity grading scale, the shift table will present directional shifts from baseline to above or below the laboratory standard normal range using the maximum increase and/or decrease observed throughout the course of treatment/observation. Both scheduled and unscheduled post-baseline values will be considered when deriving the minimum/maximum/worst post-baseline assessment.

Clinical laboratory tests will also be tabulated by the number and percentage of subjects in each abnormal category (abnormal but not clinical significant, abnormal and clinical significant) for each parameter at each scheduled visit and for the worst post-baseline assessment.

Laboratory test results will also be presented graphically in terms of box plots of absolute values over time and changes from baseline over time.

All clinical laboratory data will be listed by subject using the International System of units (SI units). Values outside the normal ranges will be flagged.

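### The SAP 8.2 laboratory tables have no cut-off or flag at post-injection chemotherapy or new anti-cancer therapy, which is allowed from 48 h, before the first scheduled post-dose blood test in 40 of 50 patients

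*Protocol*

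**What the plan says.** **Treatment around the injection.** Protocol 5.4 lets patients enter while on systemic anti-cancer treatment, with at least 72 h between chemotherapy and the injection. After the injection: "Chemotherapy administration or the start of a new anti-cancer therapy should also be held until 48hrs after IP administration".

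**Laboratory schedule.** Protocol 4.1.5: "Routine laboratory exams will be performed at all visits except at Day 2 for patients included in the non-dosimetry group". The Day 1 sample is taken before the injection (Protocol 4.2.2 and the schedules in 4.5). For the non-dosimetry group, Protocol 4.3 adds that "Day 7±1 is an optional FU physical visit and can be replaced by a phone call". The dosimetry group has laboratory tests on Days 2, 7 and 14, and the Synopsis places Day 2 at 24 h after injection.

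**Analysis.** SAP 8.2 gives change from baseline at each scheduled visit and summarises the minimum, maximum and last post-baseline values. It also gives shift tables "comparing baseline grade with the worst post-baseline grade". On which values count: "Both scheduled and unscheduled post-baseline values will be considered when deriving the minimum/maximum/worst post-baseline assessment". Nothing in SAP 8.2 ends, flags or stratifies these summaries at the start of other therapy. SAP 8 splits the safety tables by tumour type.

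**Therapy data.** SAP 6.4 calls a treatment prior if it started before the injection and concomitant if it was received on or after it. Cancer therapy is tabulated and listed by subject, but is not linked to the laboratory data.

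**The concern.** Safety of a single tracer dose is a secondary objective, and laboratory data are among its named parameters. There is no control arm, so a change from baseline can be read as a tracer effect only if nothing else likely to move the blood count or chemistry came between injection and draw. For most patients, the plan allows chemotherapy or a new anti-cancer therapy in exactly that interval. The grading scale in the protocol appendix is sensitive to small changes: any haemoglobin fall of up to 1.5 g/dL from baseline is already Grade 1.

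At stake is how far the laboratory tables can support a statement about the tracer. No test, error rate, primary endpoint or go/no-go rule depends on them.

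**Working it through.** **1. Number of laboratory occasions, checked against the plan's blood volumes (Protocol 4.1.5).**
- Dosimetry: 5 occasions × 16.5 mL + 8 activity samples × 1 mL = 90.5 mL, as stated.
- Non-dosimetry: 4 occasions × 16.5 mL = 66 mL, as stated. The four are Screening, Day 1, Day 7 and Day 14, so at most two are post-dose.

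**2. Group sizes (SAP 2.2).**
- Dosimetry: 5 breast + 5 prostate = 10.
- Non-dosimetry: 5 breast + 5 prostate + 10 colorectal + 10 NSCLC + 10 SCLC = 40, and 40/50 = 80%.
- Colorectal, NSCLC and SCLC: 30 patients, all non-dosimetry.

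**3. Draw times against the 48 h hold.** Day 7 and Day 14 can be read as study days (injection on Day 1) or as days after injection, so both are shown.

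| Scheduled draw | Hours after injection | Relative to the end of the hold |
|---|---|---|
| Day 2, dosimetry only | 24 | 24 h before |
| Day 7, earliest in window | 120 to 144 | 72 to 96 h after |
| Day 14, earliest in window | 264 to 288 | 216 to 240 h after |

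**4. Share of scheduled post-dose draws after the hold.**
- Dosimetry: 10 × 3 = 30.
- Non-dosimetry: 40 × 1 = 40 (every Day 7 by phone) to 40 × 2 = 80 (every Day 7 in person).
- Total: 70 to 110, of which 10 lie inside the hold.
- After the hold: 60/70 = 85.7% to 100/110 = 90.9%.

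These shares describe the schedule. They do not measure how many values follow actual therapy.

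**5. Direction of the effect.** Let A be a patient's values before the therapy and B those after it. The worst grade over both is max(worst A, worst B), which cannot be below worst A. Including B can therefore only keep or raise the grade in a shift table. Mean change by visit has no fixed direction.

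**6. Patients left if draws are limited to those before the therapy.** Let k be the number of non-dosimetry patients treated before their first post-dose draw. The documents do not give k, so it runs from 0 to 40. Assume that all 10 dosimetry patients have their Day 2 value and that there are no unscheduled draws. Then 50 − k patients keep at least one post-dose value.

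| k | 0 | 10 | 20 | 30 | 40 |
|---|---|---|---|---|---|
| Patients with a value | 50 | 40 | 30 | 20 | 10 |

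By tumour type the range is 0 to 10 each for colorectal, NSCLC and SCLC, and 5 to 10 each for breast and prostate, where the 5 dosimetry patients always contribute.

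**The case against.** **Attribution is handled through adverse events.** This stands in part. Protocol 6.1 counts abnormal laboratory tests as AEs, Protocol 6.7 makes the causality judgement weigh concomitant medication, and Protocol 6.8 records "concomitant treatments that may provide alternative explanation regarding the AEs occurrence". SAP 8.1 then tabulates drug-related events separately: "Note that drug-related AEs include the AEs which either definitely, probably, or possibly related to study drug". A reader might infer that laboratory toxicity goes wholly unattributed, and these sections do not support that. The SAP 8.2 tables themselves carry no such judgement, because their clinical-significance category is not a causality category.

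**Therapy started after injection can already be identified.** This stands. A reader might infer that SAP 6.4 hides newly given therapy. Under its two definitions, a treatment started after injection is concomitant only, while one begun earlier and continued is both prior and concomitant. What is not separated is a resumed cycle of an earlier regimen.

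**A restricted worst-grade table cannot isolate a therapy effect.** This stands. By step 5, using fewer values per patient can only keep or lower the worst grade, even if therapy has no effect. The patients who remain are also selected by treatment plan, and therapy given before injection can still act after baseline.

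**Descriptive tables of all observed values are legitimate.** Agreed, and they should stay. The shift tables are not labelled as tracer effects; the risk is in how they will be read.

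**Conclusion.** The point holds as a cheap improvement. For 40 of 50 planned patients, every scheduled post-dose laboratory value comes after the time from which chemotherapy or a new anti-cancer therapy is allowed, and the SAP 8.2 tables do not show which values followed such therapy. The Day 2 by-visit statistics of the 10 dosimetry patients lie inside the hold and are unaffected; their Day 7 and Day 14 draws are open to the same mixing.

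A reader might take 40 of 50 as the number of contaminated patients. The documents do not support that: it is the number whose schedule leaves them open to it, and the number actually treated before the first draw could be anywhere from 0 to 40. Nor do the documents show that tracer toxicity will be overstated. They show only that, if therapy intervenes, the shift tables can move in that direction alone.

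The conclusion assumes planned group sizes, the protocol schedule and no unscheduled draws.

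**What to change.** Keep all SAP 8.2 tables and leave the treatment rule alone. Add to SAP 8.2:

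1. A flag in the laboratory listing on every value drawn after the first post-injection chemotherapy or new anti-cancer therapy, counting resumed cycles of an earlier regimen.
2. A count, overall and by tumour type, of patients with a post-dose laboratory value before that therapy.
3. One supportive by-visit summary of change from baseline, limited to draws before that therapy.
4. If a restricted worst-grade shift table is also shown, a note beside it that fewer values per patient can only keep or lower the worst grade, so a difference from the full table does not by itself show a therapy effect.
5. An explicit new rule for values whose order relative to the therapy is unclear. SAP 5.4 says that "the missing component(s) will be assumed as the most conservative value possible", but its rules classify medications and AEs and do not place laboratory values before or after therapy. One workable rule is to keep such values in the restricted summary, mark them in the listing and report their number, accepting that some therapy effect may remain.

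**Cost.** SAP wording, one flag, one count and one supportive table. SAP 1 allows revision until database lock, and cancer therapy is already listed by subject. Whether the CRF records the date of the first post-injection administration, including resumed cycles, cannot be seen from the documents; if it does not, one date field or a site query is needed.

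**Downside.** The restricted set may be small, possibly empty for colorectal, NSCLC or SCLC. It is selected by treatment plan and remains exposed to therapy given before injection. It should be read only beside the full tables.
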